3.3.2.9 Sample Size Analysis

The study statistical power will be based on a two-sided Type 1 error rate of 0.05, and a Type 2 error rate of 0.20; these are commonly used criteria for study power calculations.

Hypothesis: We anticipate, based on our preliminary data, that 30% of patients will be fully adherent to PAP therapy (use >4 hours per night for >70% of the month). An improvement in adherence to 50% would represent a clinically meaningful change. Using a power analysis based on the chi-square frequency comparison, we anticipate that a sample size of 93 study participants per group will provide an adequate study power. We will increase this by 30% to factor in study attrition or loss to follow-up, thus a sample size of 120 would be adequate.

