We have conducted a preliminary analysis of the first 106 consecutive patients from the in-patient program. These 106 patients were on the Hospital of the University of Pennsylvania Cardiology units for congestive heart failure (87.4%, of which 53.3% had New York Heart Association Class 3 and 41.1% had Class 4 heart failure) or other cardiovascular conditions. Of these 106 patients, 81 (78%) were found to have sleep apnea on their diagnostic in-hospital sleep study; this is consistent with findings from other research that suggest a high prevalence of sleep apnea in heart failure patients (Javaheri et al. 1998) (Herrscher et al. 2011). Of these patients, 80% (65/81) had predominantly obstructive sleep apnea and 20% (16/81) had predominantly central sleep apnea. Patients were then started on PAP therapy the next night while in the hospital and continued on PAP therapy at home.

Readmission and Emergency Department visit rates were then monitored as the primary outcome; this occurred in 16.2% of patients within 30 days after discharge. Patients were divided into PAP full users (adherent >4 hours of use a night), partially PAP users (adherent 0 to 4 hours per night) and non-users. The readmission rates are shown in the related Figure. The most striking finding is that while 29-30% of the partial users and non-users were re-admitted within 30 days, none of the PAP full users were re-admitted ($p=0.025$). Also of note, only 34% of the discharged heart failure patients were full users of PAP—the majority of discharged patients were either non-users (30%) or partial-users (36%); this highlights the need to develop interventions to improve PAP

adherence. The manuscript related to these findings is accepted for publication in the Journal of Clinical Sleep Medicine pending revisions (peer-reviewed journal).

While these findings are provocative, it is important to highlight the numerous limitations of the above preliminary data. First, this is a naturalistic quasi-experimental study—the patients were not randomized to PAP or sham-PAP. Second, the study has a small sample size. Third, echocardiographic data and other biomarker data was not available to examine physiologic mechanisms. Fourth, follow-up readmission data and PAP adherence data was only available in 56 out of the 81 patients. Despite these limitations, we believe the above data suggests a possible role for sleep apnea treatment for reducing heart failure readmissions.

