What could explain this significant reduction in readmission rates? We hypothesize that there are two main avenues of benefit. First, treatment of sleep apnea has been shown to improve cardiac function in heart failure: one randomized trial demonstrated an increase in the left ventricular ejection fraction from $25.0+/-2.8$ to $33.8+/-2.4$ percent, reduced the left ventricular end-systolic dimension from $54.5+/-1.8$ to $51.7+/-1.2$ mm and other benefits (reduced heart rate and blood pressure) (Kaneko et al. 2003). Second, it is likely that PAP adherence is also linked to general medication adherence. Research conducted at the University of Pennsylvania has shown that PAP adherence correlates with medication adherence (Platt et al. 2010). However, this has not been noted in all studies (Villar et al. 2009).

Taken together, this suggests three intriguing possibilities. First and foremost: treatment of sleep apnea may be of significant benefit in reducing readmission rates. Second, it is possible that PAP adherence could be a surrogate measure of general medical adherence. Since PAP adherence is being monitored by available usage trackers built into the current PAP devices, this provides a low cost, seamless and wireless means of identifying patients at general increased risk for non-adherence. Thus a patient flagged as being non-adherent with PAP should also be queried for general medication and dietary adherence. Third, there remain significant problems with overall PAP adherence with rates as low as 34%—interventions that could improve adherence, such as the proposed study, could have a meaningful impact.

3.1.4. What is the importance of oxyhemoglobin saturation and why should we measure it?

While the acute stress of an apnea or hypopnea event is important, research suggests that hypoxia may have a greater impact as demonstrated by a stronger association with brain (B-type) natriuretic peptide (BNP), a measure of cardiovascular and hemodynamic stress (Gottlieb et al. 2009). This is of particular importance because, while the current PAP treatment devices have robust internal monitoring capabilities including hours of use, they do not routinely include capturing oxyhemoglobin saturation data.

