3.3. Approach

This project represents a partnership between AirCareLabs and the University of Pennsylvania Sleep Disorders Center. AirCareLabs has developed an innovative technology platform that focuses on the 30-day readmission period to create a seamless interface for patient-provider interactions and monitoring of disease metrics. The Penn Sleep Center is an internationally recognized leader in the field of sleep medicine, with over 15 active sleep medicine clinicians and an in-patient sleep consult service that, in preliminary data, has shown that sleep apnea treatment for heart failure patients has the potential to reduce readmission rates. However, the major limitation of the existing in-patient sleep consult service is the low adherence rate (approximately 30%) post-discharge, a limitation that can be effectively addressed using the AirCareLabs solution; this is the core proposition of the current protocol.

The proposed project Phase 1 includes the following key components: 1) Structured interviews with users/care providers; 2) Creating educational content; 3) Developing problem resolution care pathways; 4) Integration of Oximeter data;. The proposed project Phase II includes the following key components: 1) Integration of PAP adherence data; 2) Revising educational content and care pathways; 3) Developing risk classification criteria; and 4) Conducting a large randomized clinical trial to demonstrate effectiveness. These elements are described in more detail below.

We propose to utilize the Fast Track mechanism because the compelling preliminary data suggest the potential for a significant improvement in patient outcomes; all the elements of the program are in place to allow for implementation; and the rapid evolution of the competitive landscape relies upon a first-to-market approach to gather crucial market share to improve commercialization prospects.

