As part of their routine clinical care, patients with active heart failure exacerbation will be evaluated by the sleep in-patient consult service and undergo a portable sleep study. Those with newly diagnosed sleep apnea that elect to start PAP therapy and are adequately treated with PAP therapy will be eligible to participate in the Phase 2 clinical trial. They will undergo an informed consent session using an IRB-approved consent document. Based on our prior experience, we anticipate that approximately 75% will agree to participate. Thus to enroll 240 participants, we must approach 320 heart failure patients with diagnosed sleep apnea. Our preliminary data demonstrated that approximately 80% of admitted heart failure patients have sleep apnea, thus 400 heart failure patients will need to be screened for sleep apnea. The sleep disorders consult service has 10 new consults each week from the cardiology inpatient units for sleep apnea screening, thus approximately 500 new consults per year; we anticipate this volume will be adequate to enroll the required cohort for the Phase 2 study.

We will also recruit subjects from the Presbyterian and Pennsylvania Hospitals, following the same recruitment strategy. We will enroll subjects with a previous OSA diagnosis, who were previously unable to use CPAP. We will also submit a query to the Penn Data store, for de-identified data for the following: age, BMI, gender,

dx of hypertension and CHF, in an effort to expand our recruitment sources. We are also adding an additional recruitment site; Washington University at St. Louis, (WASU), site PI: [name]. This site will follow the same recruitment strategy as Presbyterian and Pennsylvania Hospitals.

3.3.2.7 Study Procedures:

After completing the informed consent process, study participants will complete the following study questionnaires (copies are provided in the Appendix): a) Self-Efficacy Measure for Sleep Apnea (Weaver et al. 2003), b) Self-Care of Heart Failure Index (Riegel et al. 2004), c) RAND Medical Outcomes Study Short Form (SF-36) (Ware et al. 1992), d) Epworth Sleepiness Scale (ESS) (Johns 1993). In addition, the medical chart will be abstracted by the study research coordinator to complete the Cumulative Illness Rating Scale (CIRS), gather demographic data, medications and other relevant covariates (Miller et al. 1992). They will then be randomized in a 1:1 ratio to either the AirCareSystems tablet or standard care as described below:

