3.3.2.8 Data Analysis

Descriptive Comparisons Between Intervention Groups at Baseline: Descriptive analyses will be performed in order to characterize the two study groups (AirCare and Standard Care) and to confirm that the randomization resulted in no clinically significant group differences at baseline in demographic, sleep, and other parameters. If the groups differ with regard to baseline variables and these variables are found to have significant associations with outcomes, secondary analysis of covariance will be used to investigate the degree to which estimated relative efficacy depends on these baseline differences.

Hypothesis: The AirCareLabs system will improve PAP adherence post-discharge relative to standard care. Statistical analysis method: PAP adherence will be defined as at least 4 hours of use per night on at least 70% of the study nights (thus, in a typical 30 day month, the study participant will have used it 21 nights for greater than 4 cumulative hours each night); this is consistent with Medicare PAP usage criteria. We will review the PAP adherence downloads, which provide an objective measure of adherence, to determine what percentage of patients in each study arm (AirCare vs. Standard Care) met the adherence criteria (i.e., a patient may be either adherent or non-adherent with PAP). We will utilize a chi-square frequency comparison for this primary analysis.

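### Does the 30% control adherence rate behind the sample size conflict with the 34% in the preliminary data, and does that undermine the 93 per group?

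*Combined protocol and SAP*

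**What the plan says.** Section 3.3.2.9 states "We anticipate, based on our preliminary data, that 30% of patients will be fully adherent to PAP therapy". It attaches a definition (more than 4 hours a night for more than 70% of the month), names 50% as a clinically meaningful level, and arrives at 93 per group, raised to 120 for attrition. The primary endpoint in section 3.3.2.8 is close to that definition: "PAP adherence will be defined as at least 4 hours of use per night on at least 70% of the study nights".

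The pilot is reported in section 3.1.3. The grouping is by hours only: "Patients were divided into PAP full users (adherent >4 hours of use a night". The result is that "only 34% of the discharged heart failure patients were full users of PAP", with 36% partial users and 30% non-users, and "PAP adherence data was only available in 56 out of the 81 patients".

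Later sections use round figures. Section 3.3 refers to "the low adherence rate (approximately 30%) post-discharge", section 3.3.2.11 to approximately 70% non-adherent, and section 3.4 to 30% adherent. No section derives 30% from 34% or gives a pilot rate on the trial's own definition.

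**The concern.** Both the number and the definition shift between the pilot report and the sample size section. Section 3.3.2.9 credits the pilot with 30% on a share-of-nights rule, while the pilot report gives 34% without one. In section 3.1.3 the figure of 30% belongs to the non-users, so a reader may even suspect that the wrong figure was carried over.

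The rate bears on the primary comparison. If 50% is a fixed target, the control rate alone sets the difference to be detected, and four points is a fifth of the planned 20. A control rate of 34% would then leave the trial well short of its stated 80% power, and the plan has no sensitivity table to show this.

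**Working it through.** **Inputs.** Two-sided alpha 0.05 and power 0.80 (section 3.3.2.9), so z = 1.960 and 0.842; control 30% and intervention 50% (3.3.2.9); chi-square test (3.3.2.8); 1:1 allocation (3.3.2.7); pilot rate 34% and 56 patients with adherence data (3.1.3).

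**Formulas.** Let m = (p1 + p2)/2, A = 1.960 × √[2m(1−m)] and B = √[p1(1−p1) + p2(1−p2)]. Then n per group = (A + 0.842 × B)² / (p2 − p1)², and power = Φ{[(p2 − p1)√n − A] / B}.

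**1. The plan's figure.** For 30% against 50%, A = 1.358, B = 0.678 and n = 93.0. The stated 93 is reproduced.

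**2. Control rate 34%, target held at 50%.** A = 1.368 and B = 0.689.
- At n = 93: (0.16 × √93 − 1.368)/0.689 = 0.254, so power is 60.0%.
- At n = 120: 0.559, so power is 71.2%.
- For 80% power, n = 149 per group.

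**3. Control rate 34%, 20-point gain kept (34% against 54%).** A = 1.376 and B = 0.688.
- At n = 93: (0.20 × √93 − 1.376)/0.688 = 0.804, so power is 78.9%.
- At n = 120: 88.2%.
- For 80% power, n = 96 per group.

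**4. Control rate 34%, planned odds ratio kept.** The planned odds ratio is (0.5/0.5)/(0.3/0.7) = 7/3, which turns 34% into 54.6%. Power is 81.2% at 93 and 89.9% at 120.

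**5. Range of control rates against 50%.**

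| Control rate | Power at 93 | Power at 120 |
|---|---|---|
| 25% | 94.7% | 98.3% |
| 28% | 87.4% | 94.2% |
| 30% | 80.0% | 89.0% |
| 32% | 70.7% | 81.3% |
| 34% | 60.0% | 71.2% |

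**6. What the pilot can tell.** The shares 34%, 36% and 30% fit 19, 20 and 17 of 56. These counts are inferred; other denominators fit too. The Wilson 95% interval for 19/56 is 22.9% to 47.0%, so 30% and 34% are equally tenable.

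**7. Is it rounding?** Partial users plus non-users make 36% + 30% = 66%. To the nearest ten, 66% becomes 70% and 34% becomes 30%, which are the round figures in sections 3.3 and 3.3.2.11.

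**8. Does the definition fix a direction?** Suppose the pilot's rule meant average hours. As an illustration, a patient with 8 hours on 18 of 30 nights averages 8 × 18/30 = 4.8 hours and counts as a full user, but fails the trial's rule at 18/30 = 60% of nights. A patient with 4 hours on 21 of 30 nights averages 4 × 21/30 = 2.8 hours, so is not a full user, yet meets the trial's rule. A share-of-nights rule may well lower the rate, but the documents do not settle it.

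**The case for a change.** The strongest case for a change is that the plan names 50% as its meaningful level. Taking its own reported 34% with that level lowers power from 80% to 60% at the planned evaluable number, and to 71% even with no loss at all. Rounding by four points is not harmless when it costs that much, and rounding does not explain the added share-of-nights rule. A short power table would be cheap.

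The arithmetic in this stands, and so does the observation that the plan never links the two figures. The inference is weaker. The 50% is stated next to a 30% baseline, and nothing says it would stay fixed if the baseline moved. With the absolute gain or the odds ratio kept instead, the loss is about one point or none. That 30% is the highest control rate giving 80% power at 93 is no sign of fragility either: 93 was solved for exactly that case.

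Re-tabulating the pilot would not settle the trial's control rate, because the populations differ. Section 3.3.2.6 limits entry to patients who elect PAP and are adequately treated, which could raise adherence. It also says "We will enroll subjects with a previous OSA diagnosis, who were previously unable to use CPAP", which could lower it.

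**Conclusion.** No change follows. The 30% reads as a rounded planning value; the plan introduces it as something anticipated, and it agrees with the approximate figures in sections 3.3 and 3.3.2.11. The documents do not show that it is wrong, that the true control rate is higher, or that the trial is underpowered.

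Power at 93 evaluable per group, if the control rate is 34%, runs from 60% (target fixed at 50%) through 79% (20-point gain kept) to 81% (odds ratio kept); at 25% against 50% it is 95%. These are conditional scenarios under the pooled two-proportion formula. The pilot interval additionally assumes 19 of 56.

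The planning rate does not enter the final analysis: the chi-square test compares the adherence observed in the two arms, so neither its type 1 error nor the estimated difference depends on whether 30% or 34% was assumed. Stating where the 30% comes from would be a courtesy to the reader. Whether raising 93 to 120 covers the intended loss to follow-up is a separate question.

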3.3.2. Phase 2 Plan

The goal of Phase 2 is to integrate PAP device data, refine the educational content, develop risk classification content and conduct a randomized controlled trial of the AirCareLab system in a target population of 240 patients.

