3.3.2.1 Task 2.1: PAP device data

The PAP devices collect hours of use, estimates apnea-hypopnea index through flow monitoring, and mask leak data on a nightly basis. This data is transmitted wirelessly by modems attached to each unit that connect to the cellular phone network. The large majority of Durable Medical Equipment (DME) providers offer this service since the insurance companies generally require documentation of adherence during the first three months of use to justify continued insurance coverage. This data is stored in a central server maintained by each of the major PAP equipment manufacturers, and is shared with the patient's providers through a web portal data review system. The companies also deliver this data in .csv files on a daily or weekly basis to provider groups, such as the Veterans Affairs administration, large group practices such as the Penn Sleep Center or health systems. The general data format is one row per night of use. During Phase 2, we will integrate this data into the AirCareLabs workflow and make it available to patients and providers directly through the AirCare system. We have elected to perform this in Phase 2 instead of Phase 1 because there are already several commercial platforms that allow for patients and providers to view their PAP-device data, therefore this offers less of a competitive advantage than direct integration of oximetry data, which we have therefore prioritized to Phase 1.

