3.3.2.10 Timeline for Phase 2 Tasks

| Tasks | Month 1-2 | Month 3 | Month 4 | Month 5-17 | Month 18-19 | Month 20-23 | Month 24 |
|---|-----------|---------|---------|------------|-------------|-------------|----------|
| Task 1: PAP data integration | ■ | | | | | | |
| Task 2: Refine Educational Content | ■ | | | | | | |
| Task 3: Risk Classification Criteria | | ■ | | | | | |
| Task 4: Study IRB approval | | ■ | ■ | | | | |
| Task 5a: Randomized Clinical Trial: Enrollment period | | | | ■ | | | |
| Task 5b: Randomized Clinical Trial: 6-month follow-up period | | | | ■ | ■ | ■ | |
| Task 6: Data analysis/manuscript generation (30-day readmission analysis) | | | | | ■ | | |
| Task 7: Data analysis/manuscript generation (6-month follow-up analysis) | | | | | | | ■ |

3.3.2.11 Milestones for the Phase 2 project:

1. PAP data integration: Successful oximetry PAP collection will be defined as transfer of the PAP data to the AirCareLabs central server in at least 90% of the study days.
2. Refine educational content: Study participant will be asked to rate their satisfaction with the educational content using visual analogue scales. The educational content will be revised during Task 2.2 in Phase 2. These visual analogue scales will then be repeated during the larger randomized trial (Task 2.4 in Phase 2). Successful completion of this task will be defined as a 20% improvement in study participant satisfaction scores after revising the educational content
3. Risk Classification Criteria: A minimum of ten risk classification criteria will be developed based on review of the data. In our preliminary study, we noted that approximately 70% of study participants were non-adherent to PAP therapy. Thus, successful completion of this milestone will also include the requirement that the ten risk classification criteria flag at least 60-70% of patients as being at risk for non-adherence with PAP therapy.
4. Randomized controlled trial: Successful completion of a randomized controlled trial of 240 study participants, with over 90% study questionnaire data completion.

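### The attrition allowance (93 × 1.3, stated as 120 per group) protects 80% power only for loss up to 22.5%; at 30% loss 84 per group remain and power is about 76%

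*Combined protocol and SAP*

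**What the plan says.** Section 3.3.2.9 of the combined protocol and SAP sets the design error rates: "The study statistical power will be based on a two-sided Type 1 error rate of 0.05, and a Type 2 error rate of 0.20". It assumes 30% adherence under standard care and takes 50% as the clinically meaningful target. On a chi-square comparison it concludes that "a sample size of 93 study participants per group will provide an adequate study power". The allowance for loss follows: "We will increase this by 30% to factor in study attrition or loss to follow-up, thus a sample size of 120 would be adequate".

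The 120 is per group. Randomisation is 1:1 (section 3.3.2.7), and section 3.3.2 describes a trial "in a target population of 240 patients".

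No expected loss rate is given apart from the 30% in that sentence. Section 3.3.2.8 determines adherence from the PAP downloads and does not say how a patient without a download is counted.

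**The concern.** Adding 30% to a sample size does not offset losing 30% of it. The sentence contains one percentage, ties it to attrition or loss to follow-up, and concludes that 120 is adequate. The natural reading is that the Type 2 error of 0.20 still holds when 30% of patients are lost, and it does not.

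This sentence supports the power claim for the primary adherence comparison, which is the only comparison the plan powers. If loss exceeds what 120 per group can absorb, the trial runs below its stated power, and nothing in the plan tells the reader where that limit lies.

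**Working it through.** **Inputs.** Two-sided α = 0.05, Type 2 error 0.20, adherence 30% versus 50% (all section 3.3.2.9); uncorrected chi-square test (sections 3.3.2.8 and 3.3.2.9; the plan mentions no continuity correction); equal groups (section 3.3.2.7); 240 patients in total (section 3.3.2).

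**Step 1: reproduce 93.** With p̄ = (0.30 + 0.50)/2 = 0.40,

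n = [1.960·√(2 × 0.40 × 0.60) + 0.8416·√(0.30 × 0.70 + 0.50 × 0.50)]² / 0.20²

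= (1.3579 + 0.5708)² / 0.04 = 92.999, so 93 per group. This matches the plan.

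**Step 2: reproduce 120.** 93 × 1.3 = 120.9. The plan writes 120, an increase of 120/93 − 1 = 29.0%. So the inflation used was n × (1 + 0.30), rounded down.

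**Step 3: what 30% loss would require.** To keep 93 after losing 30%: 93/(1 − 0.30) = 132.9, so 133 per group (266 in total).

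**Step 4: what 120 covers.** 1 − 93/120 = 0.225, so 93 remain for loss up to 22.5%.

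**Step 5: power at other loss rates.** Patients without a download are left out, and m are evaluable per group:

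power = Φ{[0.20·√m − 1.3579]/√0.46}

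| Loss from 120 per group | Evaluable per group (m) | Power (normal approximation) | Power (exact enumeration) |
|---|---|---|---|
| 0% | 120 | 89.0% | 89.4% |
| 10% | 108 | 85.6% | 85.4% |
| 20% | 96 | 81.2% | 80.9% |
| 22.5% | 93 | 80.0% | 79.9% |
| 25% | 90 | 78.7% | 79.3% |
| 30% | 84 | 75.8% | 75.9% |
| 31% | 83 | 75.3% | 75.1% |

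For m = 84: 0.20 × √84 = 1.8330; (1.8330 − 1.3579)/0.6782 = 0.7005; Φ(0.7005) = 0.758.

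**Step 6: is loss above 22.5% plausible?** The documents point both ways.

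- In the preliminary cohort (section 3.1.3), "follow-up readmission data and PAP adherence data was only available in 56 out of the 81 patients". That is 25/81 = 30.9% missing.
- For the trial, section 3.3.2.1 says of the nightly PAP data: "This data is transmitted wirelessly by modems attached to each unit that connect to the cellular phone network". This suggests lower loss, although section 3.1.3 says that units in the earlier inpatient programme were also linked by wireless modem.
- The trial milestone in section 3.3.2.11 is "Successful completion of a randomized controlled trial of 240 study participants, with over 90% study questionnaire data completion". Another milestone there asks for PAP data transfer on at least 90% of study days. Neither is a target for the share of patients with an evaluable download.

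**Step 7: sensitivity to handling.** Suppose patients without a download were counted as non-adherent. As an assumption, take equal loss in both arms and 30%/50% adherence among those retained. Then n stays at 120 but the rates shrink. At 30% loss they become 0.30 × 0.70 = 0.21 and 0.50 × 0.70 = 0.35, and power is about 68%. At 22.5% loss they become 0.2325 and 0.3875, and power is about 74%. On this basis power falls below 80% at about 15% loss.

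**The case against.** The strongest reply is that the plan did what it said. It announced a 30% increase and applied one, apart from dropping 0.9 of a patient per group, which changes power before loss only from 89.3% (121) to 89.0% (120). It never forecasts 30% loss and never says that power holds at 30% loss. Read literally, it adds a margin of 29%, which is adequate for any loss up to 22.5%.

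The 31% comparator is also weak. It comes from naturalistic clinical care, not from consented trial participants, and it counts readmission and adherence data jointly, so PAP data alone may have been missing in fewer patients. The primary endpoint covers about one month, so dropout before the six-month visit need not remove a patient from it. The 90% milestones suggest that the team expects good data capture. Finally, the 22.5% limit presupposes that patients without a download are excluded, which the plan does not state.

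Much of this stands, and it is why the point is conditional and minor. It does not rescue the sentence. The 30% is the only attrition figure given, and adequacy is asserted directly from it. If 30% is the loss allowed for, the claim is wrong by the plan's own error rate. If a lower loss is meant, it is not stated and adequacy cannot be checked. Counting patients without a download as non-adherent makes the shortfall larger.

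**Conclusion.** The concern holds. The base figure of 93 per group is right. The statement that 120 per group is adequate after a 30% allowance is wrong as written if 30% is the loss to be covered. Leaving out patients without a download, and with the plan's 30% versus 50% adherence rates, 120 per group keeps 80% power for loss up to 22.5%. Beyond that the shortfall is about 1 percentage point at 25% loss and about 4 points at 30%, and it is nil below the limit. If loss is 10% or less, the sample size is more than adequate. Severity is minor: a modest and conditional loss of power, with no effect on the analysis method.

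**What to change.** Keep 240 patients. Replace the last sentence of section 3.3.2.9 with:

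> We will enrol 120 per group (240 in total). Counting patients with a PAP download, this retains 93 evaluable per group, and 80% power, for loss up to 22.5%; at 30% loss 84 remain and power is about 76%.

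Beside it, state the loss rate expected, so that the reader can see which case applies. These figures rest on leaving out patients without a download. If the sponsor intends to count them differently, the figures must be recalculated on that basis.

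The cost is one replaced sentence and one stated rate. No patients are added and the analysis does not change; the power claim becomes openly conditional on loss.
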